- If any laboratory changes are noted in cycle 1, and deemed clinically significant for TLS by the investigator, no additional venetoclax doses should be administered until resolution. TLS prophylaxis may need to be continued with subsequent cycles based on the ongoing risk of development of TLS.
- Drug interruption for up to 48 hours following transient chemical changes and laboratory TLS may be allowed and will not require a dose reduction. If the TLS has not resolved within 48 hours, then the dose should be reduced.
- 4.7 Completion of Phase I The phase I portion will define the DLTs, MTD and RP2D of
 the combination treatment. Dose escalation will proceed in standard '3+3' design (see
 Statistical Methods section). Once the MTD is established (or if the MTD is not reached with
 800 mg of venetoclax), the phase II portion of the study will commence.

• 4.8 Definition of DLT -

A DLT will be defined as any of the following adverse events that cannot be considered primarily related to the underlying malignancy, or a comorbid condition, occurring:

- For patients without recent ponatinib exposure, between day 8 and day 35 of cycle 1 (with the exception of hematologic toxicity which may be assessed up to day 49 of cycle 1)
- For patients with recent ponatinib exposure, between day 1 and day 28 of cycle 1 (with the exception of hematologic toxicity which may be assessed up to day 42 of cycle 1)

Any ≥ grade 3 non-hematologic toxicity with the following exceptions:

- Grade 3 alopecia
- Grade 3 nausea, vomiting, diarrhea with electrolyte abnormalities lasting less than 48
 hours that are not clinically significant and that does not require total parenteral
 nutrition (TPN), tube-feeding, or hospitalization
- Infection, unless the infection resulted from unexpectedly complicated by the degree
 or duration of myelosuppression in the absence of persistent leukemia.

Patients who receive at least a full course of therapy will be considered to be evaluable for toxicity/DLT and will not be replaced unless the PI determines that further additional patients at that dose level are required for safety purposes.

Hematologic toxicity will be defined as:

- For patients without recent ponatinib exposure, failure to recover ANC > 500/μL or platelet count > 25,000/μL by day 49.
- For patients with recent ponatinib exposure, failure to recover ANC > 500/µL or platelet count > 25,000/µL by day 42.

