10. STATISTICAL METHODOLOGY

This is a single arm, open label, phase I/II study to assess the MTD and the efficacy of the combination regimen of venetoclax, ponatinib and corticosteroids in patients with relapsed/refractory Ph+ ALL.

Phase I: The primary objective is to determine the optimal dosing and schedule of the combination regimen. This aim will consist of a phase I trial to determine the maximum tolerated dose (MTD) of venetoclax when given in combination with ponatinib and dexamethasone. A standard 3+3 dose escalation design will be employed: Two dose levels of venetoclax will be explored. Patients will be treated in cohorts of size three to six and the dosage will be escalated if the clinical toxicity is acceptable. A dose-limiting toxicity (DLT) is defined in "Definition of DLT" in section 4.8.

The design is constructed to reduce the chance of escalating the dose when the probability of DLT is high, and increase the chance of escalating the dose when the probability of DLT is low. The MTD is defined as the highest dose level where a DLT occurs within at most one out of six patients treated. The escalation scheme is as follows:

- (1) If none of the initial three patients in a cohort experiences a DLT, then a new cohort of three patients will be treated at the next higher dose level.
- (2) If one of the three patients in a cohort experiences a DLT, then up to three additional patients will be treated at the same dose. Escalation will continue if only one of the six patients experiences DLT.
- (3) If two or more patients in a cohort experience DLT, then the MTD will have been exceeded, and no further dose escalation will occur. The previous dose level will be considered the MTD.
- (4) If only three patients were treated at a dose level under consideration as the MTD, then up to three additional patients will be accrued. If no more than one of the six patients at that dose level experience a DLT, then that dose level will be confirmed as the MTD. If two or more patients in that cohort experience DLT, then the previous dose level will be studied in the same fashion.

The MTD is defined as the highest dose studied for which the observed incidence of DLT is less than 33%. Frequencies of toxicities will be tabulated according to the NCI Common Toxicity Criteria. Patients will be continued to be followed for one year for evidence of late toxicity.

Table 1 below gives the probabilities of dose escalation based on true DLT risk in the 3+3 design.

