					T	rue DLT ra	ate		
	10%	20%	30%	40%	50%	60%	70%	80%	90%
Probability of									
escalation	0.91	0.71	0.49	0.31	0.17	0.08	0.03	0.01	0.001

A minimum of 6 patients and a maximum of 12 patients will be enrolled to the phase I portion of the trial.

Phase II: The primary objective is to determine the overall response rate, defined as the rate or CR + CRi occurring at the end of 2 cycles of treatment. A total of up to 26 patients will be in the phase II part including patients who received the MTD dose level in the phase I portion and those enrolled in the phase II portion of the study. The target overall response (OR) rate is 60%. This regimen of the combination treatment will be considered worthy of further investigation if it elicits an increase in OR to 60% with

acceptable toxicity. A >15% drug-related grade 4-5 toxicity rate is considered unacceptable. Thus, interim monitoring rules, assuming the prior distributions below, were constructed that meet the following two conditions,

- 1) Stop if $Prob[p(OR, E) < 0.60 \mid data] > 0.975$, or
- 2) Stop if $Prob[p(TOX, E) > 0.15 \mid data] > 0.8$,

where p(OR, E) and p(TOX, E) are the true OR and toxicity rates for the combination treatment. The first rule provides for stopping the study if the data suggest that it is unlikely (i.e., probability < 2.5%) that OR rate of the combination treatment is greater than 0.6. The second condition will stop the study early if excessive therapy-related grade 4-5 toxicity (>15%) is highly probable (i.e., probability >80%) for the combination treatment. Monitoring for toxicity and futility will not begin until 6 patients have been evaluated, and cohort size for future evaluations is 2.

The monitoring rule for the toxicity rate, based on these assumptions and monitoring conditions above is found in Table 2. For example, accrual will cease if 2 or more patients experience toxicities among the first 6 patients. Toxicities will be continually monitored and will count towards this stopping rule if they occur while the patient is still on study.

Table 2. Stop accrual if there are this many drug-related grade 4-5 toxicities among the number of patients evaluated					
# patients evaluated	# patients with toxicities				
6	2-6				
8-10	3-10				
12-16	4-16				
18-20	5-20				
22-24	6-24				
26	Stop due to maximum sample size				

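### The stated phase I size of 6 to 12 does not fit rule (4) in section 10, and section 4.7 leaves open whether 800 mg needs three or six patients before phase II opens

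*Combined protocol and SAP*

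**What the plan says.** Section 4.3 lists three venetoclax levels: -1 (200 mg), 1 (400 mg, the start) and 2 (800 mg). Section 10 says "Two dose levels of venetoclax will be explored".

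Section 10 defines the MTD twice:

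- "The MTD is defined as the highest dose level where a DLT occurs within at most one out of six patients treated".
- "The MTD is defined as the highest dose studied for which the observed incidence of DLT is less than 33" per cent, with no number of patients attached.

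Rule (4) in section 10 covers a level that has only three patients: "If only three patients were treated at a dose level under consideration as the MTD, then up to three additional patients will be accrued". The level is confirmed on this condition: "If no more than one of the six patients at that dose level experience a DLT". With two or more DLTs, the level below is studied in the same way.

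On size, section 10 states: "A minimum of 6 patients and a maximum of 12 patients will be enrolled to the phase I portion of the trial".

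Section 4.7 refers to the statistical section for the 3+3 rules. It then starts phase II when an MTD is established, "or if the MTD is not reached with 800 mg of venetoclax), the phase II portion of the study will commence".

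Phase I patients treated at the MTD count among the 26 for phase II (section 10). Table 2 stops accrual on drug-related grade 4-5 toxicity, from six evaluated patients and then every two. A DLT under section 4.8 also includes most grade 3 non-hematologic toxicity.

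**The concern.** Suppose 800 mg gives 0/3 DLTs. Rule (1) sends the trial to a higher level, and none exists. Section 4.7 describes this as an MTD that has not been reached, so a reader could hold that 800 mg is not a dose under consideration as the MTD and that rule (4) does not apply. The observed incidence is 0%, which meets the second definition. Two cohorts of three also make a phase I total of 6, the stated minimum. Read together, these would let phase II open at 800 mg on three patients. Rule (4) would ask for six.

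At stake is how many patients support the dose under the DLT rule. After 0/3 the one-sided 95% upper bound on the DLT rate is 1 - 0.05^(1/3) = 63%; after 0/6 it is 1 - 0.05^(1/6) = 39%.

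The size statement matters separately. A cap of 12, if enforced, would cut off the step-back to 200 mg that rule (4) provides for. If 800 mg and then 400 mg both fail at six patients, all 12 are used and none remain for level -1.

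**Working it through.** **1. The plan's own figure.** With p the true DLT rate and q = 1 - p, the chance of passing a level on 0/3, or on 1/3 followed by 0/3, is q³ + 3pq²·q³. For p = 10% to 50% this gives 0.906, 0.709, 0.494, 0.309 and 0.172, which matches the escalation table in section 10. The same formula is the chance that 800 mg goes forward on the three-patient reading.

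**2. The two definitions.** At six patients they agree: 1/6 = 16.7% passes both and 2/6 = 33.3% fails both. At three, 0/3 = 0% meets the second, while the first, which counts six patients, is not met. 1/3 = 33.3% fails the second.

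**3. Phase I totals, all paths enumerated.**

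| Rules applied | Totals when a dose is selected |
|---|---|
| Rule (4), levels 1 and 2 only | 9, 12 |
| Rule (4), level -1 available | 9, 12, 15, 18 |
| No rule (4), level -1 available | 6, 9, 12 |

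Under rule (4), the shortest path that selects 800 mg is 0/3 at 400 mg plus six at 800 mg, so 3 + 6 = 9. A total of 6 arises only when no level is tolerated, for example two or more DLTs in three at 400 mg and again at 200 mg (3 + 3). The path to 18 is 0/3 at 400 mg, failure at six at 800 mg, 400 mg expanded to six and failing, then six at 200 mg. The stated range of 6 to 12 is reproduced exactly when rule (4) is left out. It also equals 2 × 3 to 2 × 6.

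The plan gives no DLT rates by dose, so the chance of exceeding 12 under rule (4) needs assumptions:

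| Assumed DLT rates at 200/400/800 mg | Chance of more than 12 patients |
|---|---|
| 5/10/20% | 0.7% |
| 10/20/30% | 3.1% |
| 10/20/40% | 4.0% |
| 15/30/50% | 6.4% |
| 30/40/50% | 6.0% |

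**4. Acceptance of 800 mg once it is opened.** Under rule (4) the chance is q³(q³ + 3pq²) + 3pq²·q³.

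| True DLT rate at 800 mg | Three-patient reading | Rule (4) | Difference (points) |
|---|---|---|---|
| 10% | 0.906 | 0.886 | 2.0 |
| 20% | 0.709 | 0.655 | 5.3 |
| 30% | 0.494 | 0.420 | 7.4 |
| 40% | 0.309 | 0.233 | 7.6 |
| 50% | 0.172 | 0.109 | 6.3 |

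Only the last two rows lie above the plan's 33% limit.

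**5. Credit for Table 2.** The difference comes from trials with 0/3 and then two or three DLTs in patients 4 to 6. Let f be the share of DLTs that are drug-related grade 4-5. The plan does not give it, so it is an assumption shown over its range. At the first look (stop at two or more of six) the part that survives is q³[3p²q(1 - f²) + p³(1 - 3f² + 2f³)]. For the later looks, let each further patient have such an event with probability p·f, independently, and apply the Table 2 limits: 3 at 8-10 patients, 4 at 12-16, 5 at 18-20 and 6 at 22-24.

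| f | 40%: after first look | 40%: after all looks | 50%: after first look | 50%: after all looks |
|---|---|---|---|---|
| 0 | 7.6 | 7.6 | 6.3 | 6.3 |
| 0.25 | 7.0 | 6.6 | 5.7 | 5.1 |
| 0.5 | 5.4 | 3.4 | 4.3 | 1.9 |
| 0.75 | 2.9 | 0.7 | 2.3 | 0.2 |
| 1 | 0 | 0 | 0 | 0 |

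These figures (percentage points) assume that 800 mg is opened. That chance is 0.91 to 0.49 if the true rate at 400 mg is 10% to 30%. At f = 0.5, with all looks, the products are 1.7 to 3.1 points at 40% and 1.0 to 1.8 points at 50%. Grade 4-5 events that are not DLTs would lower them further.

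**The case against.** The case for leaving the plan alone has real weight. The two definitions agree at six patients, and rule (4) deals with a level that has only three. Section 10 treats the dose carried into phase II as the MTD, so 800 mg carried forward is naturally a dose under consideration as the MTD. Section 4.7 points to section 10 for the rules, and its parenthesis says when phase II starts without waiving any of them. The range 6 to 12 is a planning figure for two levels, and its upper end is right for those two. All of this stands. It makes the six-patient reading the more natural one, but it does not explain the minimum of 6 or provide for the listed level -1.

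A reader might infer that the plan authorises 800 mg on three patients and then exposes up to 26 - 6 = 20 more to a dose that rule (4) would reject, without a check. The documents do not support that. No sentence adopts the three-patient rule. Patients 1 to 6 at 800 mg form the first Table 2 look, and further looks follow every two patients. The investigator may add patients at a level for safety (section 4.8), and individual dose holds, SAE reporting and IND office summaries continue. What no cohort rule would catch on the three-patient reading is mainly grade 3 non-hematologic DLTs in patients 4 to 6.

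Nor is requiring six patients a clear safety gain. It rejects 800 mg 7.6 points more often at 40%, but also 7.4 points more often at 30%, a rate below the plan's limit.

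**Conclusion.** The point holds as a minor inconsistency. The stated phase I size does not match rule (4), whether or not the dispute over 800 mg is settled: selecting a dose takes at least 9 patients, and using level -1 can take 15 or 18. Totals above 12 are uncommon, about 1% to 6% under the assumed DLT rates. On the top dose, the plan most naturally requires six patients, but section 4.7, the second MTD definition and the minimum of 6 leave 0/3 available as a reading. The cost of that reading is at most 7.6 points of extra acceptance at a true DLT rate of 40% and 6.3 at 50%. With Table 2 credited, it falls to anywhere from those values down to zero, depending on f.

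**What to change.** Make three wording changes:

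- **Section 4.7:** state that phase II opens at 800 mg only after six DLT-evaluable patients at that level with no more than one DLT, citing rule (4).
- **Section 10, MTD:** keep only the definition of at most one DLT in six patients.
- **Section 10, size:** give 9 to 12 patients when a dose is selected from levels 1 and 2, and up to 18 if level -1 is used. Note that a smaller total is possible only if no level is tolerated.

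Compared with the three-patient reading, up to three more patients are treated under phase I rules, and they count toward the 26 if 800 mg is confirmed. If accrual pauses while they are assessed (the plan does not say), the delay is one DLT window: 28 days from the start of venetoclax, or up to 42 for count recovery. A tolerable 800 mg dose is accepted somewhat less often: 0.66 against 0.71 at a true DLT rate of 20%, and 0.42 against 0.49 at 30%.

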 - o Moderate and strong CYP3A inducers and inhibitors are discouraged during venetoclax administraton. If a patient requires use of CYP3A inducers, use with caution. In many instances, such as antifungal prophylaxis with "azole" therapy in neutropenic patients, CYP3A inhibitors are required in ALL patients. Venetoclax should be administered at 50% dose reduction in the setting of moderate CYP3A inhibitors (i.e. isavuconazole, ciprofloxacin, diltiazem), and 75% dose reduction in the setting of strong CYP3A inhibitors (i.e. voriconazole), with the exception of posaconazole in which dose reduction should be approximately 83% (e.g. dose reduction to 70mg if patient would normally be taking 400mg). The venetoclax dose reduction should continue for the duration of co-administration. In the event the co-administered CYP3A inhibitor is discontinued, the assigned venetoclax dose should be resumed 2-3 days after discontinuation. During the venetoclax ramp-up, these agents must be held; however, they may be started or resumed 24 hours after the highest planned dose of venetoclax is given, along with the appropriate dose reduction of venetoclax as above.
 - o Non-hematological toxicity If grade 3 or 4 non-hematologic toxicity is attributable to venetoclax, dose interruption of venetoclax is required. Patients who experience drug-related grade 3 non-hematological toxicity may be given a subsequent course one dose level below the previous course, but the patient must have recovered to grade ≤1 before start of the next course. If a patient has drug-related grade 4 non-hematological toxicity, he/she may receive a subsequent course at one reduced dose level after resolution of toxicity to grade ≤1, only if approved by the PI based on the clinical significance of the toxicity and only if patient has had derived a benefit from the therapy. The dose of venetoclax can be decreased during a cycle, at the discretion of treating physician and PI, for chronic grade 2 non-hematological toxicity. Other dose modifications may be considered as clinically indicated with documentation and approval of the PI. The dose reduction guidelines for venetoclax are in the table below:

Current Venetoclax	Reduced Dose
Dose	
800mg	400mg
400mg	200mg
200mg	100mg
100mg	50mg
50mg	20mg

20mg	Hold venetoclax
------	-----------------

o Hematologic toxicity

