7.3. CRITERIA TO STOP TREATMENT

- Failure to achieve CR/CRi after 2 cycles of treatment, unless the patient is deemed to be deriving clinical benefit (e.g. blast reduction not meeting criteria for CR/CRi) as assessed by the treating physician and PI
- 2. Unacceptable toxicity judged to be related to therapy by the investigator, as defined by the NCI Common Toxicity Criteria (irreversible or prolonged (> 42 days) grade 4 hematological toxicity or grade 4 non-hematological toxicity thought to be related to ponatinib or venetoclax), unless it has been been judged by the treating physician and PI that the patient is achieving clinical benefit.
- 3. Non-compliance by the patient with protocol requirements or patient's request to be removed from the study.
- Relapse, defined as >5% bone marrow blasts not attributed to hematopoietic recovery, occurring after initial response to therapy

Patients coming off treatment due to the above issues will continue to be followed for survival outcomes.

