Monitoring the OR rate, based on the above assumptions and monitoring conditions is found in Table 3. For example, accrual will cease if no patients experience an overall response in the first 6 patients treated.

Table 3. Stop accrual if there are th number of patients evaluated	is many response (i.e., # patients with overall response) among the	
# patients evaluated	# patients with overall response	
6	0	
8	0-1	
10	0-2	
12	0-3	
14	0-4	
16	0-5	
18	0-6	
20	0-7	
22	0-8	
24	0-9	
26	Stop due to maximum sample size	

Multc Lean Desktop (version 2.1.0) was used to generate the toxicity and futility stopping boundaries and the operating characteristics table (Table 3). In order to utilize the software for the design, a 60% constant rate and beta (1.2, 0.8) priors were assumed for the standard treatment response rate and experimental treatment response prior distribution, respectively. In addition, a 15% constant rate and beta (0.3, 1.7) priors were assumed for the standard treatment toxicity rate and experimental treatment toxicity prior distribution, respectively.

The probability of stopping the study early if the true OR of the combination treatment was 60% and the true toxicity rate was 15% was 39.24%. Probabilities of stopping early for high true toxicity rates (i.e., 40%) were 98.27% when the true OR was 60% and 99.79% when true OR rate was 30%.

True Toxicity Rate	True OR	Prob(stop the trial early)
0.10	0.30	0.9028
	0.40	0.6445
	0.50	0.3561
	0.60	0.2064
	0.70	0.1688
0.15	0.30	0.9256
	0.40	0.7278
	0.50	0.5070
	0.60	0.3924
	0.70	0.3636
0.2	0.30	0.9506
	0.40	0.8193
	0.50	0.6727
	0.60	0.5966
	0.70	0.5775
0.3	0.30	0.9861
	0.40	0.9490
	0.50	0.9076
	0.60	0.8861
	0.70	0.8808
0.4	0.30	0.9979
	0.40	0.9922
	0.50	0.9860
	0.60	0.9827
	0.70	0.9819

Secondary objectives include: the rate of minimal residual disease negativity by PCR for BCR-ABL1 transcripts, proportion of patients proceeding to ASCT, relapse-free survival, overall survival, and the safety of the combination regimen.

The investigator is responsible for completing toxicity/efficacy summary reports and submitting them to the IND office Medical Affairs and Safety Group for review. These should be submitted as follows:

- Phase I: A toxicity summary must be submitted after the first 3 evaluable patients, complete 1
 cycle of study treatment, and every 3 evaluable patients thereafter, IND office approval must be
 obtained prior to advancing/changing dose levels.

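### Could section 4.8's evaluability sentence let an early DLT drop out of the 3+3 count?

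*Combined protocol and SAP*

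**What the plan says.** The only statement on DLT evaluability and replacement is in section 4.8: "Patients who receive at least a full course of therapy will be considered to be evaluable for toxicity/DLT and will not be replaced", followed by an exception allowing the PI to ask for more patients at a dose level for safety. A full course is not defined.

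Section 4.8 defines a DLT by type of event and calendar window. For one group the window is "For patients without recent ponatinib exposure, between day 8 and day 35 of cycle 1"; for patients with recent ponatinib exposure it is day 1 to day 28. Count recovery is judged up to day 49 or day 42 respectively. No minimum amount of treatment is attached.

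In section 10, rule (1) turns on the initial three patients in a cohort. Rule (2) reads "If one of the three patients in a cohort experiences a DLT, then up to three additional patients will be treated at the same dose". Rule (3) stops escalation at two or more. On the MTD: "The MTD is defined as the highest dose level where a DLT occurs within at most one out of six patients treated". The size statement is "A minimum of 6 patients and a maximum of 12 patients will be enrolled to the phase I portion of the trial".

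The word *evaluable* returns in section 10 in the reporting schedule. A toxicity summary is due after the first three evaluable patients have completed a cycle, and then: "cycle of study treatment, and every 3 evaluable patients thereafter, IND office approval must be" obtained before dose levels change.

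**The concern.** The patients on whom section 4.8 is silent are the ones who matter most in a dose-finding phase. Most non-hematologic events of grade 3 or higher in the window are DLTs, and the plan expects such events to disrupt treatment. Section 4.5 says: "If grade 3 or 4 non-hematologic toxicity is attributable to venetoclax, dose interruption of venetoclax is required". Section 7.3 lists among its stopping criteria "grade 4 non-hematological toxicity thought to be related to ponatinib or venetoclax", with a clinical-benefit exception. A patient with a severe toxicity in the second week may therefore never receive a full course.

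If only full-course patients were evaluable, that patient could be replaced and the DLT would leave the count. One DLT among the first three would become 0 of 3, and the dose would go up without expansion to six. Two such patients, both replaced by patients without a DLT, would allow escalation after 2 DLTs in 5 treated. The bias always runs towards escalation, and the MTD sets the phase II dose. The use of *evaluable* in the reporting step that precedes IND office approval lends the reading some colour.

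**Working it through.** **1. The plan's own table.** With every DLT counted and true DLT rate p, escalation needs 0 of 3, or 1 of 3 followed by 0 of 3:

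P(escalate) = (1−p)³ + 3p(1−p)² × (1−p)³

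At p = 0.40 this is 0.216 + 0.093 = 0.309. For p = 0.1 to 0.9 it gives 0.906, 0.709, 0.494, 0.309, 0.172, 0.082, 0.032, 0.009 and 0.001. The section 10 table shows 0.91, 0.71, 0.49, 0.31, 0.17, 0.08, 0.03, 0.01 and 0.001. All nine agree, so the table assumes that every DLT counts.

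**2. The rules applied to the two troubling cases.**

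| Case | Section 10 as written | If 4.8 is read as *only* full-course patients |
|---|---|---|
| 1 of the first 3 stops in week 2 with a DLT | That patient is one of the initial three: 1 of 3, rule (2), expand | Replaced by a patient without a DLT: 0 of 3, escalate after 4 treated |
| 2 of the first 3 stop early with a DLT | 2 in the cohort: rule (3), no escalation | Both replaced: 0 of 3, escalate after 5 treated |

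The left column needs no added rule. The right column needs two steps that appear nowhere: that a patient without a full course is not evaluable, and that a patient with a DLT may be replaced.

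**3. What *evaluable* does in the reporting schedule.** It fixes when a summary is due. It does not restrict the summary to those patients, and the escalation rules and MTD definition do not use the word. The phase II bullet also uses it, tied to completing the second cycle, so it does not simply carry the 4.8 sense.

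**4. Scale of the misreading, as a hypothetical.** Let a share s of DLT patients be omitted and replaced. The documents give no value for s. Each enrolled patient then has a counted DLT with probability p(1−s), an omitted DLT with ps, or no DLT with 1−p. Escalate at 0 of 3 or 1 of 6 counted, stop at two counted DLTs, and score no escalation if an enrolment limit is reached first. Two limits are shown. Six at level 1 is an assumption that leaves six of the 12 for level 2; the protocol states only the overall 12.

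At p = 0.40:

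| s | P(escalate), limit 6 | of which after ≥2 actual DLTs | P(escalate), limit 12 | of which after ≥2 actual DLTs |
|---|---|---|---|---|
| 0 | 0.309 | 0 | 0.309 | 0 |
| 10% | 0.328 | 0.002 | 0.351 | 0.026 |
| 25% | 0.366 | 0.015 | 0.428 | 0.077 |
| 50% | 0.461 | 0.069 | 0.599 | 0.207 |

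Check without any limit: the rate among counted patients is p(1−s)/(1−ps). At s = 0.25 that is 0.30/0.90 = 0.333, and the formula in step 1 gives 0.428, as in the table.

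Both the size and the make-up of the effect depend on the assumed limit. At s = 50%, escalation after two or more actual DLTs is 0.069/(0.461 − 0.309) = 45% of the increase with a limit of 6, and 0.207/(0.599 − 0.309) = 71% with a limit of 12.

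**The case for a change.** The best argument for a change is that it is nearly free. One sentence saying that a DLT in the window counts whatever treatment was received would remove any doubt, and the count sets the phase II dose. Three points support it. No sentence says expressly that an early DLT counts. *Evaluable* is described for DLT purposes only in section 4.8. The other safeguards are partial: a grade 3 DLT need not be a serious adverse event, IND office approval does not define the count, and the phase II toxicity rule covers only drug-related grade 4-5 events.

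The silence is real, and the sentence would be harmless housekeeping at a next amendment. What does not stand is the step from silence to a wrong count. It requires reading *only* into section 4.8 and letting that override section 10, which states the escalation rules in full. Nor would the event be hidden. Section 8 puts on the case report form every drug-related event of any grade, and any event that leads to a dose modification, so an early grade 3 DLT is recorded even when it is not serious. The reviewing office sees a toxicity summary before any dose change.

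**Conclusion.** No change is needed. Section 4.8 gives a sufficient condition for evaluability and leaves the early-DLT case unstated. The DLT definition by event and date, together with section 10's counting of patients in a cohort and patients treated, settles that case in the usual 3+3 way. Followed as written, the plan expands after one early DLT in three and stops after two. No stated probability, sample size or decision rule is wrong, and the escalation table stands as printed.

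The hypothetical figures do not alter this. At a true DLT rate of 40% they run from 0.02 to 0.04 added escalation probability if 10% of DLT patients were omitted, and from 0.15 to 0.29 if 50% were. They rest on an omitted share with no source and on the enrolment limit assumed at level 1, and they describe a trial that departs from section 10. The conclusion assumes that the team applies the section 10 rules to the patients it treats, and replaces at most those who leave cycle 1 early without a DLT.
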